### 7.2. Participant Withdrawal From the Study

A participant may withdraw from the study at any time at his/her own request, or may be withdrawn at any time at the discretion of the investigator for safety, behavioral, compliance, or administrative reasons.

If a participant withdraws from the study, he/she may request destruction of any samples taken and not tested, and the investigator must document this in the site study records. If the participant withdraws consent for disclosure of future information, the sponsor may retain and continue to use any data collected before such a withdrawal of consent.

See [Table 3](#) for data to be collected at the time of study withdrawal and follow-up and for any further evaluations that need to be completed.

### 7.3. Lost to Follow-Up

A participant will be considered lost to follow-up if he/she repeatedly fails to return for scheduled visits and is unable to be contacted by the study site.

The following actions must be taken if a participant fails to return to the clinic for a required study visit:

- The site must attempt to contact the participant and reschedule the missed visit as soon as possible and counsel the participant on the importance of maintaining the assigned visit schedule and ascertain whether or not the participant wishes to and/or should continue in the study.
- Before a participant is deemed lost to follow-up, the investigator or designee must make every effort to regain contact with the participant (where possible, 3 telephone calls and, if necessary, a certified letter to the participant's last known mailing address or local equivalent methods). These contact attempts should be documented in the participant's medical record.
- Should the participant continue to be unreachable, he/she will be considered to have withdrawn from the study.

## 8. STUDY ASSESSMENTS AND PROCEDURES

### 8.1. Administrative and General Procedures

#### 8.1.1. Informed Consent Process

- The investigator or his/her representative will explain the nature of the study to the participant or his/her legally authorized representative and answer all questions regarding the study.
  - Informed consent must be obtained before any study-related procedures are conducted, unless otherwise specified by the Protocol.
  - Informed consent must be obtained using the IRB/IEC-approved version in a language that is native and understandable to the participant. A template will be provided by the sponsor or its designee. The sponsor or its designee must review and acknowledge the site-specific changes to the ICF template. The ICF must include a statement that the sponsor or its designee and regulatory authorities have direct access to participant records.
  - The ICF must contain all required elements and describe the nature, scope, and possible consequences of the study in a form understandable to the study participant.
- Participants must be informed that their participation is voluntary. Participants or their legally authorized representative will be required to sign a statement of informed consent that meets the applicable requirements and regulations for the countries in which the study is being conducted as well as the IRB/IEC or study center.
- The participant must be informed that his/her personal study-related data will be used by the sponsor in accordance with local data protection laws. The level of disclosure must also be explained to the participant.
- The participant must be informed that his/her medical records may be examined by Clinical Quality Assurance auditors or other authorized personnel appointed by the sponsor, by appropriate IRB/IEC members, and by inspectors from regulatory authorities.
- The medical record must include a statement that written informed consent was obtained before the participant was enrolled in the study and the date the written consent was obtained. The authorized person obtaining the informed consent must also sign the ICF.
- Participants must provide consent to the most current version of the ICF during their participation in the study.
- A copy of the ICF(s) must be provided to the participant or the participant's legally authorized representative.

Participants who are rescreened are required to sign a new ICF and will be assigned a new participant number.

### **8.1.2. Screening Procedures**

Screening is the interval between signing the ICF and the day the participant is enrolled in the study (Cycle 1 Day 1). Screening may not exceed 30 days. Assessments that are required to demonstrate eligibility may be performed over the course of 1 or more days during the screening process.

Procedures conducted as part of the participant's routine clinical management (eg, blood count, imaging study) and obtained before signing of the ICF may be used for screening or baseline purposes provided the procedure meets the Protocol-defined criteria and has been performed in the timeframe of the study as noted in this Protocol. For participants who are enrolled in the study, information associated with eligibility requirements must be entered into the appropriate eCRF pages.

Results from the screening visit evaluations will be reviewed to confirm eligibility before enrollment or the administration of study drug. Tests with results that fail eligibility requirements may be repeated once during screening if the investigator believes the results to be in error. For screening assessments that are repeated, the most recent available result before treatment assignment will be used to determine eligibility. Treatment should start as soon as possible but within 3 days after the date of enrollment.

See Sections [5.4](#) and [5.5](#) for information regarding screen failures and replacement of participants, respectively.

### **8.1.3. Interactive Response Technology Procedure**

Each participant will be identified in the study by a participant ID number, which is a combination of a country's abbreviation, the site ID, and the participant number. Site staff should contact the IRT to obtain the participant ID number during screening. Upon determining that the participant is eligible for study entry, the IRT will be contacted to enroll the participant.

Additionally, the IRT will be contacted on Day 1 of each cycle to update the study drug supply. Additional details are provided in the IRT Manual.

### **8.1.4. Distribution of Reminder Cards**

Participants will be provided with a reminder card at each visit. The reminder card will indicate the date/time of the next visit.

### **8.1.5. Demography and Medical History**

#### **8.1.5.1. Demographics and General Medical History**

Demographic data and general medical history will be collected at screening by the investigator or qualified designee and will include year of birth/age, race, ethnicity, medical and surgical history, and current illnesses. Medical history will include relevant medical or surgical treatment within the last 10 years that are considered to be clinically significant by the investigator.

### **8.1.5.2. Disease Characteristics and Treatment History**

A disease-targeted medical and treatment history will be collected at screening. Details regarding the participant's malignancy under study, including date of diagnosis, initial and current cancer stage, tumor histology, relevant disease characteristics, and prior treatments, including systemic treatments, radiation, and surgical procedures will be recorded.

## **8.2. Efficacy Assessments**

### **8.2.1. Tumor Imaging**

Objective assessment of tumor status is required using appropriate disease-specific techniques, and a central radiologic facility will be used to determine responses and will be logged in to the eCRF. RECIST v1.1 ([Eisenhauer et al 2009](#)) will be used, and the recommended method for measuring and following tumor burden will be CT scan to include the thorax, abdomen, and pelvis; the neck and head may be included if clinically indicated. In cases where participants are diagnosed with brain metastases prior to initiation of study, standard-of-care brain scans would be clinically appropriate. Alternative modalities (eg, MRI) may be substituted for a CT scan at the discretion of the investigator, provided that the same modality is used throughout the study and that the methodology is consistent with RECIST v1.1.

The schedule for efficacy assessments will be at screening (this will be considered the baseline scan), every 9 weeks (ie, every 3 cycles starting at Cycle 3), and then at EOT (if applicable). If a participant discontinues before the first on-treatment assessment, and the baseline imaging was performed in the 2 weeks before Cycle 1 Day 1, then an EOT assessment is not required.

Imaging should continue in 9-week intervals regardless of delays in cycle starts. For participants showing a response, a confirmatory scan may be performed a minimum of 4 weeks (per RECIST v1.1) from the previous scan. For participants showing a progression based on local radiologic review, treatment should not be discontinued until progression of disease has been determined by the ICR group unless the principal investigator believes it is in the best interest of the participant to discontinue treatment before receiving confirmation.

For participants who discontinue treatment for reasons other than disease progression, every effort should be made to continue monitoring their disease status by radiographic imaging until the start of new anticancer therapy, documented disease progression, death, or the end of the study, whichever occurs first.

### **8.2.2. ECOG Performance Status**

Eastern Cooperative Oncology Group performance status (see [Table 9](#)) will be assessed at the visits specified in [Table 3](#).

**Table 9: ECOG Performance Status**

Grade	Performance Status
0	Fully active, able to carry on all predisease performance without restriction.
1	Restricted in physically strenuous activity but ambulatory and able to carry out work of a light or sedentary nature, eg, light house work, office work.
2	Ambulatory and capable of all self-care but unable to carry out any work activities. Up and about more than 50% of waking hours.
3	Capable of only limited self-care, confined to bed or chair more than 50% of waking hours.
4	Completely disabled. Cannot carry on any self-care. Totally confined to bed or chair.
5	Dead.

Source: [Oken et al 1982](#).

#### **8.2.4. Medical Resource Utilization and Health Economics**

Medical resource utilization and health economics data, associated with medical encounters, may be assessed using data already captured in the eCRF for all participants in this study (eg, AEs, concomitant medications, procedures).

The data collected may be used to conduct exploratory economic analyses and may include:

- Number and duration of medical care encounters, including surgeries, and other selected procedures (inpatient and outpatient).
- Duration of hospitalization (total days or length of stay, including duration by wards [eg, intensive care unit]).
- Number and type of diagnostic and therapeutic tests and procedures.
- Outpatient medical encounters and treatments (including physician or emergency room visits, tests and procedures, and medications).

#### **8.3. Safety Assessments**

See Section [6.5](#) for guidelines regarding the management of relevant laboratory or other safety assessment abnormalities.

##### **8.3.1. Adverse Events**

Adverse events will be monitored from the time the participant signs the ICF until at least 30 days after the last dose of study drug or until the start of new anticancer therapy. Adverse events for enrolled participants that begin or worsen after informed consent should be recorded on the Adverse Events Form in the eCRF regardless of the assumption of a causal relationship with the study drug. Conditions that were already present at the time of informed consent should

be recorded on the Medical History Form in the eCRF. Adverse events (including laboratory abnormalities that constitute AEs) should be described using a diagnosis whenever possible rather than by individual underlying signs and symptoms.

Adverse events will be reported by the participant (or, when appropriate, by a caregiver, surrogate, or the participant's legally authorized representative). The investigator and any qualified designees are responsible for detecting, documenting, and recording events that meet the definition of an AE or SAE and remain responsible for following-up on AEs that are serious, considered related to the study drug/procedures, or that caused the participant to discontinue the study drug and/or withdraw from the study. Care will be taken not to introduce bias when detecting AEs and/or SAEs. Open-ended and nonleading verbal questioning of the participant, such as "How are you feeling?" is the preferred method to inquire about AE occurrences. Adverse events may also be detected when they are volunteered by the participant during the screening process or between visits or through physical examinations, laboratory tests, or other assessments. The definition, reporting, and recording requirements for AEs are described in Section 9.

All SAEs will be reported to the sponsor or designee within 24 hours. The investigator will submit any updated SAE data to the sponsor within 24 hours of it being available.

After the initial AE/SAE report, the investigator is required to proactively follow each participant at subsequent visits/contacts. All SAEs will be followed until resolution, stabilization, the event is otherwise explained, or the participant is lost to follow-up (as defined in Section 7.3).

### **8.3.2. Physical Examinations**

Physical examinations must be performed by a medically qualified individual, such as a licensed physician, physician's assistant, or an advanced registered nurse practitioner, as local law permits. Abnormalities identified after the first dose of study treatment constitute an AE if they are considered clinically meaningful, induce clinical signs or symptoms, require concomitant therapy, or require changes in study drug. Investigators should pay special attention to clinical signs related to previous serious illnesses.

At the screening visit, a comprehensive physical examination should be conducted. The comprehensive physical examination will include height and body weight, and assessment of the following organ or body systems: skin; head, eyes, ears, nose, and throat; thyroid; lungs; cardiovascular system; abdomen (liver, spleen); extremities; and lymph nodes; as well as a brief neurological examination.

During the study, participants will be assessed by the investigator or medically qualified designee per institutional standard of care. These assessments should be an evaluation as indicated by participant symptoms, AEs, or other findings and documented on the AE eCRF. Weight will also be assessed at each study visit.

### **8.3.3. Vital Signs**

Abnormal vital sign results identified after the first dose of study drug constitute an AE if they are considered clinically meaningful, induce clinical signs or symptoms, require concomitant therapy, or require changes in study drug/treatment.

Vital sign measurements should be taken before blood collection for laboratory tests and include blood pressure, pulse, respiratory rate, pulse oximetry, and body temperature. If vital signs cannot be taken before blood collection for laboratory tests, there must be a minimum of approximately 30 minutes from the completion of the blood collection procedures to the beginning of the vital signs collection. Blood pressure and pulse will be taken with the participant in the recumbent, semirecumbent, or sitting position after approximately 5 minutes of rest.

#### **8.3.4.      Electrocardiograms**

Single 12-lead ECGs will be obtained as outlined in the SoA (see [Table 3](#)) using an ECG machine that automatically calculates the heart rate and measures PR, QRS, QT, and QTcF intervals. All 12-lead ECGs will be performed with the participant in a recumbent or semirecumbent position after 5 minutes of rest.

The 12-lead ECGs will be interpreted by the investigator at the site to be used for immediate participant management. Additional 12-lead ECGs may be performed as clinically indicated to manage participant safety. The decision to include or exclude a participant or discontinue study treatment based on an ECG flagged as "Abnormal, Clinically Significant" is the responsibility of the investigator, in consultation with the sponsor's medical monitor as appropriate. Clinically notable abnormalities that are considered clinically significant in the judgment of the investigator are to be reported as AEs. In the event that a single QTcF is  $> 480$  milliseconds at screening, the participant may enroll if the average QTcF for 3 ECGs is  $\leq 480$  milliseconds or with approval from the medical monitor. For participants with an intraventricular conduction delay (QRS interval  $> 120$  milliseconds) at screening, the JTc interval may be used in place of the QTcF with medical monitor approval. In addition, the JTc interval should be used for all subsequent assessments.

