## 5. STUDY POPULATION

Deviations from eligibility criteria are not allowed because they can potentially jeopardize the scientific integrity of the study, regulatory acceptability, and/or participant safety. Therefore, adherence to the criteria as specified in the Protocol is essential. Prospective approval of Protocol deviations to recruitment and enrollment criteria, also known as Protocol waivers or exemptions, are not permitted.

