## 5.2. Exclusion Criteria

Participants are excluded from the study if any of the following criteria apply:

1. Prior receipt of a selective FGFR inhibitor.
2. Receipt of anticancer medications or investigational drugs for any indication or reason within 28 days before the first dose of pemigatinib. Participants must have recovered ( $\leq$  Grade 1 as per CTCAE v5.0 or at pretreatment baseline) from AEs from previously administered therapies (excluding alopecia).
3. Concurrent anticancer therapy (eg, chemotherapy, immunotherapy, biologic therapy, hormonal therapy, or investigational therapy).
4. Candidate for potentially curative surgery.
5. Current evidence of clinically significant corneal (including but not limited to bullous/band keratopathy, corneal abrasion, inflammation/ulceration, and keratoconjunctivitis) or retinal disorder (including but not limited to macular/retinal degeneration, diabetic retinopathy, and retinal detachment) as confirmed by ophthalmologic examination.
6. Radiation therapy administered for the treatment of cancer lesions within 2 weeks before enrollment/first dose of study drug. Participants must have recovered from all radiation-related toxicities, not require corticosteroids, and not have had radiation pneumonitis. Evidence of fibrosis within a radiation field from prior radiotherapy is permitted with medical monitor approval. A 1-week washout is permitted for palliative radiation to non-CNS disease.
7. Untreated brain or CNS metastases or brain or CNS metastases that have progressed (eg, evidence of new or enlarging brain metastasis or new neurological symptoms attributable to brain or CNS metastases). Participants who have previously treated and clinically stable brain or CNS metastases are eligible if there is no evidence of progression for at least 4 weeks after CNS-directed treatment, as ascertained by clinical examination and brain imaging (MRI or CT scan) during the screening period, and if they are on a stable or decreasing dose of corticosteroids for at least 1 week.
8. Known additional malignancy that is progressing or requires active treatment. Exceptions include basal cell carcinoma of the skin, squamous cell carcinoma of the skin, or *in situ* cervical cancer that has undergone potentially curative therapy.
9. Participants with laboratory values at screening defined in [Table 5](#).

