**Table 5: Exclusionary Laboratory Values**

Laboratory Parameter		Exclusion Criterion
Hematology		
a	Platelets	$\leq 75 \times 10^9/L$ (transfusion allowed with a 2-week washout period)
b	Hemoglobin	$\leq 9.0 \text{ g/dL}$ (transfusion allowed with a 2-week washout period)
c	ANC	$\leq 1.5 \times 10^9/L$
Hepatic		
d	ALT	$\geq 3 \times \text{ULN}$ ( $> 5 \times \text{ULN}$ for liver metastasis)
e	AST	$\geq 3 \times \text{ULN}$ ( $> 5 \times \text{ULN}$ for liver metastasis)
f	Total bilirubin	$\geq 1.5 \times \text{ULN}$ ( $\geq 2.5 \times \text{ULN}$ if Gilbert's syndrome or liver metastasis)
g	Alkaline phosphatase	$\geq 3 \times \text{ULN}$
Renal		
h	Serum creatinine clearance	$\leq 30 \text{ mL/minute}$ based on Cockcroft-Gault formula
Chemistry		
i	Serum phosphate	$> \text{ULN}$
j	Serum calcium	Outside of normal range or serum albumin-corrected calcium outside of the normal range when serum albumin is outside of the normal range

10. History of calcium and phosphate hemostasis disorder or systemic mineral imbalance with ectopic calcification of soft tissues (exception: commonly observed calcifications in soft tissues such as the skin, kidney tendon, or vessels due to injury, disease, or aging in the absence of systemic mineral imbalance).
11. Gastrointestinal conditions/disorders that may raise gastric and/or small intestinal pH that could interfere with absorption, metabolism, or excretion of pemigatinib.
12. Inability to swallow and retain oral medication.
13. Clinically significant or uncontrolled cardiac disease, including unstable angina, acute myocardial infarction within 6 months before Day 1 of study drug administration, New York Heart Association Class III or IV congestive heart failure, and uncontrolled arrhythmia (participants with pacemaker or with atrial fibrillation and well-controlled heart rate are allowed).
14. History or presence of an abnormal ECG that, in the investigator's opinion, is clinically meaningful. A screening QTcF interval  $> 480$  milliseconds is excluded. For participants with an intraventricular conduction delay (QRS interval  $> 120$  ms), the JTc interval may be used in place of the QTcF with medical monitor approval. The JTc must be  $\leq 340$  milliseconds if JTc is used in place of the QTcF.

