**Table 7: Guidelines for Interruption and Restarting of Study Drug (Continued)**

Adverse Event	Action Taken
• Recurrent Grade 2 toxicity	Step 1: Interrupt pemigatinib up to 2 weeks (14 days), until toxicity resolves to $\leq$ Grade 1 Step 2: If related to pemigatinib, restart pemigatinib at the next lower dose level. Monitor as clinically indicated and if AE persists, consider further dose reduction.
• Any Grade 3 toxicity	Step 1: Interrupt pemigatinib up to 2 weeks (14 days), until toxicity resolves to $\leq$ Grade 1. Step 2: Restart pemigatinib at same dose. If assessed as related to pemigatinib, restart pemigatinib at the next lower dose; monitor as clinically indicated. If AE persists for more than 1 cycle, consider a dose reduction.
• Any recurrent Grade 3 toxicity after 2 dose reductions.	Discontinue pemigatinib administration and follow-up per Protocol. (Exceptions require approval of sponsor.)
• Any other Grade 4 toxicity. • QT/QTc to $>$ 500 ms or to $>$ 60 ms over baseline.	Discontinue pemigatinib administration and follow-up per Protocol.

For participants who present with possible or confirmed SRD/RPED based on OCT, the guidelines in [Table 7](#) should be followed. It is recommended to discuss the findings with the sponsor's medical monitor before making changes to the participant's treatment.

Per CTCAE v 5.0, retinal detachment is graded as 3 (macular sparing) and 4 (macula-off), but this refers to rhegmatogenous retinal detachment (when a hole occurs in the retina). There is no grading for SRD/RPED (no hole in the macula, just fluid accumulation). Therefore, grading should be based on the CTCAE v5.0 term of retinopathy.

The starting dose of pemigatinib will be 13.5 mg QD, intermittent dosing regimen (2 weeks on treatment and 1 week off treatment). Dose reductions should follow as noted below:

- Starting dose: 13.5 mg QD intermittent dosing
- First dose reduction: 9 mg QD intermittent dosing
- Second dose reduction: 4.5 mg QD intermittent dosing

Dose reductions below 4.5mg QD are not allowed. Following a dose reduction and resolution of pemigatinib-related toxicities, a participant's dose may be returned to the starting dose at the discretion of the investigator and in consultation with the sponsor's medical monitor.

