2.1 Participant Disposition	
2.1.1	Participant Enrollment and Disposition Status
2.1.2	Participant Inclusion and Exclusion Criteria Violations

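### Protocol Section 8.3.4 lets the medical monitor admit a participant with QTcF above 480 ms, with no ceiling, although criterion 14 excludes that participant and Section 5 bars eligibility waivers

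*Protocol*

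**What the plan says.** Four places in the Protocol bear on a long screening QTcF.

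- **Section 5.2, criterion 14** sets the limit: "A screening QTcF interval $> 480$ milliseconds is excluded". It allows one substitute measure. For a QRS above 120 ms, "the JTc interval may be used in place of the QTcF with medical monitor approval", with a numeric cap: "The JTc must be $\leq 340$ milliseconds if JTc is used in place of the QTcF".
- **Section 8.3.4** takes up the case of a single screening QTcF above 480 ms and says "the participant may enroll if the average QTcF for 3 ECGs is $\leq 480$ milliseconds or with approval from the medical monitor". The sentence that follows gives the JTc route separately, with its own monitor approval.
- **Section 5** says that eligibility deviations are not allowed and adds: "Prospective approval of Protocol deviations to recruitment and enrollment criteria, also known as Protocol waivers or exemptions, are not permitted".
- **Section 6.5.1, Table 7** requires discontinuation of pemigatinib at "QT/QTc to $>$ 500 ms or to $>$ 60 ms over baseline".

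In the SAP, Appendix A plans Listing 2.1.2, "Participant Inclusion and Exclusion Criteria Violations".

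**The concern.** The approval clause in Section 8.3.4 is joined by an *or*. It is therefore an alternative to a 3-ECG mean at or below 480 ms, not an addition to it, and it matters only when that mean is above 480 ms or was never obtained. Criterion 14 excludes exactly that person. Neither section refers to the other on this point, and Section 8.3.4 gives the monitor no maximum value and no condition to apply.

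The immediate stake is who receives the drug. A participant admitted this way is followed on QTcF and starts closer to the permanent stop than criterion 14 allows, or beyond it. The second stake is reporting. The same participant is an eligibility violation if Section 5.2 is applied and compliant if Section 8.3.4 is applied, so what belongs in Listing 2.1.2 depends on which section the reader uses.

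**Working it through.** **Step 1: one test case through each provision.** Take a screening QTcF above 480 ms, a 3-ECG mean of 490 ms and QRS of 120 ms or less, so that JTc is not available.

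| Provision | Result |
|---|---|
| Section 5.2, criterion 14 | Excluded: 490 > 480 |
| Section 8.3.4, 3-ECG mean | Not met: 490 > 480 |
| Section 8.3.4, monitor approval | May enroll; no ceiling applies |
| Section 5, ban on waivers | Advance approval against a criterion is not permitted |

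These cannot all be applied to the same person.

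**Step 2: can the clause be read as the JTc route?** No. The next sentence of Section 8.3.4 already gives JTc its own monitor approval, limited to QRS above 120 ms. Read as JTc, the clause in the QTcF sentence would be redundant.

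**Step 3: does the protocol put monitor approvals inside the criteria elsewhere?** Yes, twice in Section 5.2. Criterion 6 says "Evidence of fibrosis within a radiation field from prior radiotherapy is permitted with medical monitor approval", and criterion 14 does the same for JTc. The QTcF limit in criterion 14 carries no such wording.

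**Step 4: margin to the Table 7 stop.** Table 7 has two limits, 500 ms and 60 ms over baseline. For any baseline above 500 − 60 = 440 ms the 500 ms limit is reached first, so the margin is 500 − entry QTcF.

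| Entry QTcF (ms) | Margin (ms) |
|---|---|
| 480 (highest that criterion 14 allows) | 20 |
| 485 | 15 |
| 490 | 10 |
| 500 | 0 |
| 505 | −5 |

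**Step 5: what a smaller margin means with single ECGs.** Section 8.3.4 specifies single 12-lead ECGs. The documents give no within-person SD, so I assume 5, 10 or 15 ms, with normal reading error, no drug effect and a true QTcF equal to the stated value. Then

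P(one ECG > 500) = 1 − Φ((500 − QTcF)/SD).

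| True QTcF (ms) | SD 5 | SD 10 | SD 15 |
|---|---|---|---|
| 480 | 1 − Φ(4) = 0.003% | 1 − Φ(2) = 2.3% | 1 − Φ(1.33) = 9.1% |
| 490 | 1 − Φ(2) = 2.3% | 1 − Φ(1) = 15.9% | 1 − Φ(0.67) = 25.2% |
| 500 | 50% | 50% | 50% |

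The plan states no figure of its own to reproduce here. The conflict in Steps 1 to 3 does not depend on Step 5.

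**The case against.** The best defence is that Section 8.3.4 is itself protocol text. Applying an exception that the protocol writes down is arguably not a deviation, so the ban in Section 5 would not be engaged, and what remains is a missing cross-reference. Eligibility rules do sit outside Section 5.2: repeat testing is in Sections 5.4 and 8.1.2. Section 8.3.4 also restates the JTc route without its 340 ms cap, which suggests it was meant to be read alongside criterion 14. This weakens the argument from Section 5 but does not reconcile the two sections. Section 5.2 excludes a participant who meets any listed criterion, and criterion 14 neither contains the exception nor points to it.

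Second, clinical judgment remains in place. Criterion 14 also excludes ECG abnormalities that the investigator finds clinically meaningful, criterion 24 excludes conditions posing a significant risk, and Section 8.3.4 makes the investigator responsible for ECG-based inclusion. Entry at or above 500 ms would need both investigator and monitor to accept it, so that end of the range is an extreme. This stands as to likelihood. However, none of these safeguards sets a number, and Table 7 governs dosing, not entry.

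Third, the probabilities rest on assumed SDs, and a participant who properly qualifies at 480 ms already carries up to 9.1%. That is correct. They illustrate the loss of margin and do not estimate harm in this trial.

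Fourth, little follows for the analysis. The full analysis set and safety population take in every enrolled, dosed participant, and under SAP Section 10.1 the per-protocol population is not generated. That also stands, and it limits the effect on reporting to the violations listing.

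**Conclusion.** The concern holds. Section 8.3.4 opens an uncapped route by monitor approval past a limit that criterion 14 states without that exception, in a protocol that says eligibility waivers are not permitted. The conflict is established from the text alone.

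Criterion 14 guarantees a margin of at least 20 ms to the 500 ms stop; the approval route guarantees none. Under the assumptions in Step 5, going from a true QTcF of 480 to 490 ms raises the chance that one ECG reads above 500 ms from 2.3% to 15.9% at an SD of 10 ms. Over SDs of 5 to 15 ms the ranges are 0.003–9.1% and 2.3–25.2%.

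The practical reach is small. SAP Section 10.1 reports fewer than 10 participants enrolled at termination, and the documents do not show that the route was used. No analysis set or efficacy estimate changes. It should be corrected as a matter of participant safety and consistent eligibility reporting.

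**What to change.** In Section 8.3.4, delete the monitor-approval alternative from the QTcF sentence. In criterion 14, add the 3-ECG rule, for example: *A screening QTcF > 480 ms is excluded; if a single QTcF is > 480 ms, the mean of 3 ECGs decides.* Leave the JTc route with its 340 ms cap and the Table 7 limits unchanged.

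Deletion is preferable to moving the approval into criterion 14 with a new cap. It keeps the limit the protocol already sets and avoids choosing a higher figure that the documents do not support. Placing the 3-ECG rule in the criterion also makes it the specific rule for QTcF. Section 8.1.2 otherwise allows one repeat of a failed test and lets the most recent result decide, which does not fit a mean of three.

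The cost is one clause removed and one added, with no new data. The only people turned away are those whose 3-ECG mean stays above 480 ms and who do not qualify on JTc, and criterion 14 already excludes them. With enrollment ended, the remaining use is to classify any such participant consistently in Listing 2.1.2 and to keep the clause out of later protocols.
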